## $\pi$ / 6 (anteroposterior width X cephalocaudal width X transverse width).

Prostate volume calculated by pre-programmed equipment will be accepted if the anteroposterior, cephalocaudal and transverse are also outputted and recorded in the eCRF. If the prostate volume calculated by pre-programmed equipment is utilised for a subject, then the same equipment and hence calculator, must be used for the duration of the subject's participation in the study.

For each individual subject, all TRUS procedures should be performed by the same technique and, if possible, the same individual and, ideally, that individual will not be responsible for soliciting adverse events or assessing relatedness of adverse events to study medication. At Visit 1b, if the prostate volume is <30cc the patient should not be randomized to the double blind phase.

The diagrams below show how the maximum dimension of each section will be determined. The transverse (T) dimension and the anteroposterior (AP) dimension are to be measured in the transverse plane. Scanning in the sagittal (longitudinal) plane would allow for the cephalocaudal (L) measurement of the prostate length from the apex to the bladder neck.

Transverse Scan

Sagittal Scan

[TZ=transition zone; PZ=peripheral zone; CZ=central zone; SV=seminal vesicle; AFS=anterior fibromuscular stroma]

#### 7.2.2.3. Urinary Flow Measurement

Measurements of urinary flow will be conducted using a Uroflow Meter (details will be provided in the study procedures manual) at Screening Visit 1a/b, Baseline (Visit 2) and every scheduled 26 week clinic visit post-randomisation thereafter during the treatment period.

The following assessments will be collected:

• peak (maximum) flow  $(Q_{max})$  at a voided volume  $\ge 125$  ml at all visits

#### • voided volume (ml)

During screening, the patient should undergo a urine flow assessment at the same visit, i.e. at Pre-screening (Visit 1a), if possible. If a subject is unable to perform the urine flow at the first screening visit (Visit 1a), then the subject can retry at Visit 1b, prior to starting the placebo run-in period. The subject will only be eligible to be enrolled in the study if Qmax is >5mL/sec and  $\le 15$ mL/sec and the voided volume is  $\ge 125$ mL for one assessment. If the voided volume is less than 125mL at any assessment, the subject should be instructed to drink more water until his bladder is full when the test can be repeated. During the study, if the repeat voided volume is less than 125ml the first voided volume will be recorded in the eCRF.

All uroflow traces should incorporate subject identifiers, date and time of assessment and should be signed and dated by the investigator and retained with the subjects study records. During continuous use, the correct functioning of the uroflow meter will be checked once a week (especially if moved) and appropriate actions taken to ensure good maintenance of the machine.

Due to the circadian changes in urinary flow measurements in BPH subjects, study visits for an individual subject should be conducted consistently in either the morning or afternoon hours to assess all urinary flow measurements. Subjects should be instructed to drink at least 2 glasses of water 2-3 hours prior to their clinic visit and to keep drinking every 15 minutes filling the bladder. Also, subjects must be instructed to abstain from using any alpha adrenergic agonist, cholinergic or anticholinergic agents including antihistamines or decongestants within 48 hours prior to conducting this test. In addition subjects must also abstain from taking selective beta 3-adrenoceptor agonist (mirabegron) for over-active bladder syndrome for two weeks prior to this test. If the subject did not adhere to these guidelines, study procedures should not be performed and the visits should be rescheduled.

When conducting uroflow measurements, the funnel should be kept at the subject's knee level and the printout away from the subject's view. Subjects should be blinded from all uroflow measurement data throughout the study.

#### 7.2.2.4. Definition of Other Efficacy Measures

Other efficacy measures are noted in Section 7.2.1.2. The following provides clinical definition for these measures.

Renal insufficiency is defined as >=50% sustained rise in baseline serum creatinine and >=1.5mg/dL; BPH-relatedness will be assessed by the investigator.

Urinary tract infection (UTI) is defined as symptomatic infection of 10^5 cfu/mL during the study; recurrent UTI is defined as two or more UTI episodes during the study. BPH-relatedness will be assessed by the investigator.

Incontinence (overflow or urge) is defined as socially or hygienically unacceptable involuntary leakage of urine). BPH-relatedness will be assessed by the investigator.

## 7.2.2.5. End of Study Treatment Assessments

During the study period that is between the scheduled visits, if a subject discontinues study treatment permanently after Visit 2 (post-randomisation) for any reason, other than lost to follow-up, the investigator should make every effort to schedule a visit by the subject to the study site and complete the following assessment:

- Concomitant medications
- Adverse events
- Physical exam including vital signs, DRE and qualitative breast examination
- Obtain blood samples for hematology, clinical chemistry and PSA determinations
- Administer health outcome questionnaires (IPSS, BHS,BII and PAS-SFI)
- Administration of C-SSRS questionnaire
- Record any episodes of AUR, and, BPH-related prostatic surgery or minimally-invasive/non-surgical interventions
- Record any episodes of UTI/urosepsis, urinary incontinence (first episode or consistent worsening), and renal insufficiency
- Retrieve any unused double-blind study medication, assess compliance and record date of last dose of study medication
- Discuss the biannual follow-up phone call schedule
- Complete subject eCRF

If the decision for a subject's study treatment discontinuation is made during a regularly scheduled visit, the procedure that are stated above should be completed, in addition to any scheduled procedure that is not listed above.

## 7.2.3. Short Messaging Service Reminder System

To help with the retention of the subjects and planning of their scheduled follow up throughout the study, subjects will be sent text messages via their mobile telephone, or email reminders, regarding their scheduled appointments. Sites will gain consent from the subject in the ICF before enrolling their mobile phone number or e-mail address into the secure short messaging service (SMS) reminder system. The system will then transmit text messages or e-mails to the subject in the local language regarding their next appointment.

• Subject participation in the SMS reminder system is voluntary and refusal to participate will not indicate withdrawal from the clinical study. Refusal to participate will involve no penalty or loss of benefits to which the subject would otherwise be entitled. The SMS reminder system may not be available for all study sites or countries. Even if available, study sites or countries may choose not to participate in the SMS reminder system. All text message/e-mail content will be reviewed and approved by the IRB/IEC prior to use.

## 7.3. Safety

## 7.3.1. Endpoints

- Change in total serum PSA from baseline
- Vital signs
- Post-void residual volume
- Clinical laboratory measurements (including haematology, chemistry)
- Adverse events (including AUR or BPH-related surgery and Prostate Cancer and prostate biopsy)
- Physical examination: digital rectal examination (DRE) and qualitative breast examination
- An assessment of suicidality

See Section 7.4 for a complete description of adverse event assessments.

# 7.3.2. Medical History, Concomitant Medications, ECG, Physical Examination

**A medical history** will be obtained at Pre-screening Visit 1a with particular attention paid to the following:

- Approximate time (date) LUTS first noted by patient; time since diagnosis of BPH; previous usage of alpha-1-adrenoreceptor antagonists and/or phytotherapy.
- A thorough review of body systems, both past or current conditions including conditions of interest, smoking history, alcohol, and an assessment of sexual activity/sexual dysfunction;
- Family history of premature cardiovascular disease
- Pharmacotherapy, chronic use of any medication (prescribed and over the counter, including dietary supplements);
- History of allergies or idiosyncratic reactions to drugs;
- Family history of prostate cancer
- Family history of male/female breast cancer

Concomitant medications will be assessed at every clinic visit. Use of dietary supplements (i.e. selenium, Vitamin E) during the study is discouraged but not prohibited. All concomitant medications and use of dietary supplements will be recorded in the eCRF. Additional details related to concomitant medications are addressed in Section 6 of this protocol.

**A good quality 12-lead ECG recording** will be obtained for each subject at Screening Visit 1b. The subject should rest supine for 5 minutes before the 12-lead ECG is recorded. Additionally a rhythm strip will be obtained to assess for presence of

arrhythmias. The ECG must be calibrated, labelled and initialled by the person performing the recording. The ECG tracing must be signed and dated by the examining physician to indicate review and any clinically important abnormalities reported on the appropriate page of the eCRF. A copy of the ECG tracing will remain with the subject's medical notes at the site.

A complete physical examination will be conducted at Screening Visit 1b and will include measurements of height, weight, blood pressure, digital rectal exam, and a qualitative breast exam (nipple tenderness and/or palpable breast tissue).

Weight will be measured on a standard calibrated scale. Subjects should be dressed in light indoor clothing without shoes. Weight will be documented in kilograms to the nearest tenth of a kilogram using the following conversion factor:

Pounds 
$$x = 0.4536 = kg$$

For height measurements, subjects should be measured without shoes. Height will be documented to the nearest tenth of a centimeter using the following formula:

Inches 
$$x = 2.54 = centimeters$$

The physical exam will be performed by a licensed physician. Full details of the physical examination will be recorded in the source documents at the site.

## 7.3.3. Physician's assessments and vital signs

At each clinic visit prior to dispensing study drug, a physician will assess the subject's continued eligibility and safety.

Vital signs (blood pressure followed by pulse) will be assessed at Screening Visit 1b, Baseline Visit 2 and at each scheduled 13 week clinic visit thereafter. The subject must be sitting quietly for at least 5 minutes before measurements are taken. No other procedures will be performed during this 5 minute stabilisation period. Pulse rate will be measured for 30 seconds.

In addition, a physical examination will be conducted at Visit 4 (26 weeks post-randomisation) and at 26 week intervals thereafter during the treatment period, and will include a digital rectal exam and a qualitative breast examination (nipple tenderness and/or palpable breast tissue).

The physical exam will be performed by a licensed physician. Full details of the physical examination will be recorded in the source documents at the site.

## 7.3.4. Clinical Laboratory Assessments

Blood samples for all laboratory assessments throughout the study will be collected prior to undergoing any clinical procedures. In order to determine each subject's eligibility to participate in the study, the results of the screening clinical laboratory tests must be assessed by the principal investigator or designee prior to study drug administration. Any

subject having a laboratory result that falls outside the specifications noted in the inclusion or exclusion criteria will be excluded from the study.

Out-of-threshold range values indicated on the clinical laboratory test reports must be assessed as "not clinically significant" (NCS), "clinically significant" (CS), or "repeat" (to indicate a repeat test will be performed). If any laboratory values are deemed clinically significant, the subject must return to the clinic for re-evaluation. All clinically significant changes from baseline will be followed until resolution or stabilization as determined by the principal investigator or designee. The results of all clinical laboratory tests must be assessed by the investigator in order to determine each subject's eligibility to continue in the study.

Haematology and clinical chemistry assessments will be performed at Pre-screening (Visit 1a) to establish eligibility for enrolment and annually post-randomisation at Visits 6, 10. Additionally, a blood draw for HBsAG, and Hepatitis C Antibody should be performed at Visit 2 (baseline).

Laboratory Assessment	Visit Frequency
Hematology	Visits 1a,6, 10
Clinical Chemistry	Visits 1a, 6, 10
PSA	Visits 1a, 4, 6, 10
HBsAG and Hepatitis C Antibody	Visit 2

## 7.3.4.1. Haematology and Clinical Chemistry

Haematological and biochemical analyses will be conducted by a central laboratory designated by GlaxoSmithKline. The following tests will be performed:

Haematology	Clinical Chemistry (Serum)
Total WBC Count	Glucose
Platelet Count	
Haemoglobin	Sodium
RBC	Potassium
	Total protein
PSA (Serum)	Total bilirubin
Total PSA	BUN or urea
	Albumin
HBsAG and Hepatitis C Antibody	ALT (SGPT)
	AST (SGOT)
	Alkaline Phosphatase
	Creatinine

All clinical laboratory analyses will be conducted at a Central Laboratory selected by GSK. Laboratory data will be electronically transferred from the contract Central Laboratory to GSK or their designee. A printout of results will be transmitted via facsimile to the investigator or designee and must be retained in each subject's study file. In addition to the facsimile results, the investigator will be notified of alert values (out-of-threshold range values or exclusions) by telephone.

RM2010/00134/05

## 7.3.4.2. Prostate Specific Antigen (PSA)

Total serum PSA concentrations will be assessed at Pre-screening Visit 1a and post-randomisation at Visit 4, (Month 6), and annually at Visits 6 and 10. For total PSA, the actual value will be reported at Pre-screening; an adjusted value will be reported for all assessments after 6 months of treatment – see below.

A number of clinical situations (e.g. prostatitis, biopsy, prostatic abscess) can cause transient rises in PSA. Therefore, blood samples for evaluating PSA levels must be collected within the study-defined time windows and prior to performing any clinical procedures (i.e. TRUS and DRE). If a situation arises requiring interim intervention, PSA determinations must be postponed for a period of 1 month following any procedure performed on the prostate and for 3 months following initiation of treatment for acute bacterial prostatis.

Screening PSA results will be reported immediately to the investigators to determine eligibility of study subjects. All post-baseline PSA levels will subsequently be reported following blinding adjustment of the PSA result (where appropriate) as described below.

In order to maintain investigator blinding to study treatment, an independent reviewer who is unblinded to the PSA results as well as the drug random code, will adjust PSA values for appropriate participants. After a subject completes six month of treatment, PSA results will be reported to the principal investigators using the following methods: (1) for subjects on tamsulosin monotherapy, the actual PSA value will be reported; (2) for subjects receiving combination therapy, the PSA value will be multiplied by two (x 2) to account for the known effect of 5ARI's on reducing PSA (data from Phase IIIa and CombAT studies of dutasteride in BPH patients demonstrated a decrease in serum PSA levels by approximately 50% after 6 months of treatment). In dutasteride-treated subjects receiving combination therapy, the doubled PSA value will be randomly stated as the doubled value or a value 0.1 units higher or lower, so that all doubled values expressed to one decimal place will not automatically be reported as an even number.

**Note**: Dutasteride reduces total serum PSA concentration by approximately 40% following 3 months of treatment and by approximately 50% following 6, 12, and 24 months of treatment. PSA measurements should not be performed prior to 6 months of treatment because of the variable effect of dutasteride on serum PSA during this time. Although discouraged, if an additional PSA measurement outside the scheduled assessments is necessary, it should be assayed through the study central laboratory.

Central laboratory, study sites, and monitors will remain blinded to treatment assignments throughout the duration of the study.

## 7.3.5. Post Void Residual Volume

Post void residual volume will be measured suprapubically by ultrasound (immediately following the urinary flow measurement) at Pre-screening Visit 1a/1b (if Qmax inclusion criteria not met at Visit 1A), at Baseline (Visit 2) and at 26 week clinic visits thereafter during the treatment period. Subjects with post void residual volumes >250mL as

2016N305272\_00 ARI114265

measured at Screening (Visit 1a/1b) should be excluded from participating in the study. The time of bladder scan and the time of the preceding void will also be recorded.

## 7.3.6. Acute Urinary Retention

A subject is considered to have acute urinary retention (AUR) when he is unable to urinate and requires bladder catheterisation.

At Visit 2 (Baseline) and each scheduled 13 week clinic visit post-randomisation, the investigator will record in the designated section of the eCRF any incidence of AUR the subject experiences during his participation in the study.

Any occurrence of AUR should not be captured as an adverse event unless considered by the investigator to be more severe than expected for the subject's condition or unrelated to BPH. See Section 7.4.1 and Section 7.4.7. If in the investigator's opinion, the event meets the definition of serious as outlined in Section 7.4.2 then the event must be reported as an SAE (see also Section 7.4.7.).

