# 6.3. Treatment after Discontinuation of Study treatment or Discontinuation of Study

Post study treatment will not be provided as part of the protocol. Upon discontinuation from assigned study treatment, subjects may receive additional (non protocol) therapy at the discretion of the treating physician. The investigator is responsible for ensuring that consideration has been given to the post-study care of the patient's medical condition whether or not GSK is providing specific post-study treatment.

If a subject discontinues study treatment permanently after Visit 2 (post-randomisation) for any reason, other than lost to follow-up, the investigator should make every effort to complete the following activities listed below: (Note: the subject has the right to refuse any further contact for study-related follow-up information).

- End of Study Treatment Assessments as outlined in Section 7.2.2.5.
- Biannual follow-up for clinical events via telephone contact every 6 months relative to baseline visit (Visit 2) until the 2 year anniversary of randomisation. Any occurrence of death, AUR, BPH-related prostatic surgery or minimally-invasive/non-surgical intervention for BPH, prostate cancer /biopsy reported after premature withdrawal of study treatment, and outcomes of sexually related adverse events reported during the treatment period, should be fully documented in the eCRF and source documents. The purpose of the collection of these data is to more fully document study endpoints and related events.

No additional study activities other than those that are stated above are planned after a subject's permanent discontinuation from study treatment

A subject is considered a 'withdrawal' from the study when no study procedure has occurred, no follow-up has been performed and no further information has been collected for this subject from the date of withdrawal/last contact.

The primary reason for permanent discontinuation of study must be documented in the subject's medical records and eCRF.

Subjects who are withdrawn from the study after randomisation will not be replaced.

In the event that a subject is prematurely discontinued from the study treatment or withdraw from the study at any time due to an AE (as defined in Section 7.4.1, "Definition of an AE") or SAE (as defined in Section 7.4.2, "Definition of an SAE"), the procedures described in Section 7.4.7 ("AEs and SAEs") must be followed.

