# 7.4.2.5. Disease-Related Events and/or Disease-Related Outcomes Not Qualifying as SAEs

A disease-related event is an event generally associated with the disease under study and is not typically associated with the use of the investigational product. In this study, disease-related events will be captured as part of efficacy assessments and hence will be reported as AEs or SAEs only under the following circumstances:

- If a disease-related event is considered by the investigator to be more severe than expected for the subject's condition, but does not meet the definition of serious as outlined in Section 7.4.2, the event should be reported as an AE.
- If a disease-related event is considered by the investigator to be more severe than expected for the subject's condition and meets the definition of serious as outlined in Section 7.4.2, the event must be reported as an SAE.
- If a disease-related event is life-threatening or fatal, regardless of the investigator's assessment of severity expected for the subject's condition, the event must be reported as an SAE.

Disease-related events for this study are listed below.

- BPH symptoms (incomplete emptying, frequency, intermittency, urgency, weak stream, straining, nocturia)
- Changes in Qmax
- Changes in subject's response to questions asked in the IPSS and humanistic assessments.

- Acute urinary retention
- Urinary tract infection/urosepsis
- Urinary incontinence (overflow/urge)
- BPH-related Renal insufficiency

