## 7.4.7. Time Period and Frequency of Detecting AEs and SAEs

The investigator or site staff is responsible for detecting, documenting and reporting events that meet the definition of an AE or SAE.

AEs will be collected from the start of the placebo run-in phase until the end of the two year study period.

SAEs will be collected over the same time period as stated above for AEs. However, any SAEs assessed **as related** to study participation (e.g., investigational product, protocolmandated procedures, invasive tests, or change in existing therapy) or related to a GSK concomitant medication, will be recorded from the time a subject consents to participate in the study up to the end of the two year study period. All SAEs will be reported to GSK within 24 hours, as indicated in Section 7.4.8.

After discontinuation of study treatment, the investigator will monitor all AEs/SAEs that are ongoing until resolution or stabilization of the event or until the subject is lost to follow-up. Investigators are not required to actively seek information on adverse events occurring after the follow-up contact, but may report any adverse event that they believe may be related to investigational product regardless of when the event occurs.

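### The protocol gives conflicting SAE-capture rules for hospitalised urinary retention of expected severity, and for new events after treatment is stopped

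*Protocol*

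**What the plan says.** **AUR.** Protocol 7.3.6 opens with an exclusion: "Any occurrence of AUR should not be captured as an adverse event unless considered by the investigator to be more severe than expected", or unrelated to BPH. Its next sentence, which leaves the judgement to the site physician, says that where "the event meets the definition of serious as outlined in Section 7.4.2 then the event must be reported as an SAE". Hospitalisation is criterion (c) of the definition of serious in 7.4.2.

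Section 7.4.2.5 names AUR among the disease-related events and says that these "will be reported as AEs or SAEs only under the following circumstances". Two of the circumstances lead to an SAE. The first requires that the event be "more severe than expected for the subject's condition and meets the definition of serious". The second drops the severity condition, but only in this case: "If a disease-related event is life-threatening or fatal, regardless of the investigator's assessment of severity expected for the subject's condition".

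**After stopping treatment.** Section 7.4.7 says that "AEs will be collected from the start of the placebo run-in phase until the end of the two year study period", and gives SAEs the same window. Section 4.2.1 makes clear that a man who stops treatment need not leave the study. Section 6.3 plans an end-of-treatment assessment and six-monthly telephone calls. The calls cover death, AUR, BPH surgery or other BPH intervention, prostate cancer or biopsy, and the outcome of sexual AEs already reported. It then states: "No additional study activities other than those that are stated above are planned after a subject's permanent discontinuation from study treatment".

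**Use in the analysis.** Section 9.3.7.2 compares the proportion of subjects with at least one serious AE between arms by Fisher's exact test in the ITT population.

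**The concern.** The count of subjects with a serious AE should not depend on which section a site happens to follow. In both places it can.

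For AUR, two sites with identical patients could report differently while each complies with part of the protocol. The situation is realistic, since 7.5.4 and 9.3.8 plan to collect and tabulate hospital admissions for AUR. AUR is also a secondary efficacy outcome on which the arms may differ: section 1.1 reports a lower risk of AUR and BPH surgery with combination than with tamsulosin at four years in the earlier trial. Inconsistent coding could therefore move the SAE difference.

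For men off treatment, a new non-fatal SAE falls inside the collection window, yet no planned contact asks about it. An analysis plan cannot recover an event that was never solicited.

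**Working it through.** **1. AUR rules side by side** (BPH-related AUR)

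| Case | Literal 7.3.6 | 7.4.2.5 |
|---|---|---|
| Not serious, expected severity | not an AE | not an AE |
| Serious, worse than expected | SAE | SAE |
| Life-threatening or fatal | SAE | SAE |
| Hospitalised, not life-threatening, expected severity | SAE | not an SAE |

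Only the last row conflicts.

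**2. Possible effect on the SAE comparison.** The protocol gives no AUR, admission or SAE rate, so everything here is assumption. Take 293 per arm, other SAEs equal in both arms at 8%, 12% or 16%, and no overlap with AUR. Add hospitalised, expected-severity AUR as follows:

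- 1% tamsulosin against 0.5% combination: 3 against 1 men; difference 2/293 = 0.7 points
- 2% against 1%: 6 against 3 men; 3/293 = 1.0 point
- 4% against 1.5%: 12 against 4 men; 8/293 = 2.7 points

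Under 7.4.2.5 the difference is 0 in each case. Under literal 7.3.6 it is 0.7 to 2.7 points in favour of combination, with Fisher p from 0.35 to 0.91 across the background rates.

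**3. Follow-up rules side by side.** A new non-fatal SAE outside the 6.3 list, in a man off treatment, is inside the general window of 7.4.7. It is not on the call list of 6.3. The paragraph of 7.4.7 on the time after discontinuation requires follow-up only of events already ongoing. Section 6.3 refers to 7.4.7 only for men who stop because of an AE or SAE, so capture may also depend on why a man stopped.

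**4. Person-time affected.** Inputs from 9.2.1: difference 1.8, SD 6, 90% power, 20% discontinuation; two-sided 0.05 from 9.1.

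- The plan's figure reproduces: n = 2 × (1.960 + 1.282)² × 6² / 1.8² = 233.5, so 234 per arm; 234 / 0.80 = 292.5, so 293 per arm and 586 in total.
- Planned follow-up: 586 × 2 = 1172 person-years.
- Men stopping treatment: 0.20 × 586 = 117.
- Person-years off treatment = 117.2 × 2 × f, where f is the average share of the two years still to run (assumed):
  - f = 0.25: 59 (5%)
  - f = 0.50: 117 (10%)
  - f = 0.75: 176 (15%)

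**The case against.** **The 7.3.6 sentences may be meant in sequence.** On that reading the event in the second sentence is only an AUR that has already passed the first test. This agrees with 7.4.2.5 for BPH-related AUR and avoids the oddity of an SAE that is not an AE. It is possible, but the text does not say it. Nor does it settle matters that 7.4.2.5 is a subsection of 7.4.2: 7.4.2.5 itself lists severity and the 7.4.2 definition of serious as two separate conditions.

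**The bias is limited.** Randomisation is 1:1 by site (5.4) and sites are blinded to dutasteride or placebo (5.5, 7.3.4.2), so a site's reading applies to both arms alike. AUR and its admissions are also recorded separately, so affected cases can be identified. This stands. A reader might infer that the conflict decides the Fisher result, or that every man with AUR changes status. The documents support neither. If 1 to 4% of 293 had any AUR (assumed), that would be 3 to 12 men per arm, but only the hospitalised, expected-severity subset could switch.

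**Section 7.4.7 has its own rule for the time after discontinuation.** It speaks of ongoing events, does not require active search after the follow-up contact, and allows later reports of suspected related events. Read as the specific rule, it comes close to 6.3. Deaths are asked about on the calls, AEs are assessed at the end-of-treatment visit, and 7.4.8 leaves detection methods to the study procedures manual, which is not shown. This narrows the gap, but the general two-year sentence remains and still conflicts with the closed list.

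**Two further inferences are tempting.** One is that the ITT denominator presumes two years of follow-up for everyone; no section says so. The other is that the cardiac-failure imbalance in section 1.1 makes the gap urgent. The same section reports no such events among 325 Asian subjects, and this trial enrols only Asian men.

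**Conclusion.** Both conflicts are in the current protocol text and should be resolved, but the consequences are modest.

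For AUR, the classification of one type of case depends on the section followed. The number is unknown and is at most the hospitalised, expected-severity subset. The effect is inconsistent coding in both arms, which could shift the SAE difference if AUR differs by arm but is unlikely to change the test result.

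For men off treatment, new non-fatal SAEs are in the window but not solicited. This affects about 117 men and up to roughly 5 to 15% of planned person-years. The figure rests on the planned 20% discontinuation and on assumed timing. It is lower in practice, because men lost to follow-up or refusing contact cannot be asked under either section.

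The primary endpoint and the time-to-AUR endpoint are not affected, since AUR has its own eCRF section and is on the call list.

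**What to change.** - Reconcile 7.3.6 with 7.4.2.5 into a single SAE reporting rule for AUR that states explicitly what applies to a hospitalised case of expected severity. Which rule is adopted is for the sponsor to decide.
- Reconcile 6.3 with 7.4.7. Either add a question on any new SAE to the six-monthly calls, or restate the window in 7.4.7 so that it matches what 6.3 collects after discontinuation.

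The cost is clarified wording. If the question is added, there is also a little more call time and a few more SAE forms. How the SAE tables are laid out can stay with the reporting and analysis plan.
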